7.4 Subject Withdrawal

Subjects may withdraw from the study at any time without impact to their care.

7.4.1 Data Collection and Follow-up for Withdrawn Subjects

There will be no attempts to collect data from participants who have withdrawn consent. However, the Sponsor will retain all data collected for each subject prior to withdrawal.

7.5 Early Termination Visits

Subjects who terminate their participation early will receive no further follow up.

8 STUDY EVALUATIONS AND MEASUREMENTS

8.1 Demographics

The following demographic information will be obtained

- Date of birth
- Gender
- Race

8.2 Medical Record Review (Part 2 only)

The Medical Record review will be conducted to provide a description of the enrolled patients to aid in the interpretation of the reported outcomes of the study.

- Height
- Weight
- Admitting diagnosis and co-morbidities related to DVT/VTE risk, including:
Heart Failure; diabetes; known thrombophilic states (protein C, protein S, or antithrombin deficiency; thrombotic thrombocytopenic purpura; hemolytic-uremic syndrome; activated protein C resistance; factor V Leiden thrombophilia, prothrombin gene mutation; antiphospholipid antibody; hyperhomocysteinemia); post-partum status (within 6 months); estrogen therapy (oral contraceptive or hormone replacement); active malignancy (treatment within the past 6 months or palliation); history of malignancy (within the past 5 years, other than non-melanoma skin cancer); paralysis or immobilization of a lower or upper extremity related to stroke or injury before this hospital admission; hospitalization in the past 3 months for any reason (excluding this hospital admission); trauma (including acute spinal cord injury, hip fracture, pelvic fracture, femoral fracture and tibial, fibular, knee or other fractures below knee); recent surgery (in the last 48h); acute stroke (in this index hospital admission); prior DVT or VTE; tumor or malignancy; hospitalization in previous 3 months
- Length of stay
- Use of pharmacological thromboprophylaxis and types of agents if used
- Use of pharmacological anticoagulant/antiplatelet therapy, type, dose
- Injury Severity Score (ISS)

8.3 Laboratory Tests (Part 2 only)

Of the initial labs drawn by the clinical team upon patient admission to the hospital, results from the complete blood count (hemoglobin, platelets) and coagulation panel (PT, PTT, INR) will be recorded on the case report form.

8.4 Vital Signs (Part 2 only)

Body temperature, heart rate, respiratory rate, and blood pressure will be measured by standard procedure at the time of subject enrollment.

8.5 Hemodynamic ultrasonography

A hemodynamic ultrasonography will be performed (when feasible) by certified technician/radiologist or physician trained in venous valve sinus imaging. The study specific ultrasound procedure SOP will be followed. All efforts will be made to conduct the ultrasound procedure with the assigned device even if subject is no longer clinically wearing the assigned device but agrees to wear for ultrasound procedure.

The following parameters will be measured both at rest and during the inflation period of the OsciPulse device and the calf ICD: centerline flow velocity, centerline flow, [REDACTED]

Video clips of the 2D color Doppler exams will be collected by the imaging personnel and transferred via a data storage device to [REDACTED] study personnel. The data will then be blinded and sent to Dr. [REDACTED], an expert in ultrasound image quantification, to perform the analysis and quantify the above parameters which will be provided back to the [REDACTED] team for data entry.

8.6 Questionnaires

For healthy subjects a questionnaire will assess tolerability of the device and open-ended feedback on the device. Part 2, a questionnaire with a 100-mm visual analog scale will be used to assess tolerability. The questionnaire will assess the comfort level, level of noise, and interference with sleep and movement. The questionnaire will also consist of a question to evaluate compliance and binary-response questions for the subject's future preferences.

8.7 Safety Evaluations

Adverse events will be monitored over the course of the intervention.

8.8 Compliance Monitoring

Compliance monitoring will be carried out by research staff from [REDACTED], and will consist of inquiring with the subject if the devices were removed for any period of time during the 3 hour study period. If the device was removed the [REDACTED] staff will note the reason and duration of the interruption.

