4.2.2 Study Intervention Phase

Part 1: Enrolled healthy subjects will have the OsciPulse device applied by study or medical personnel according to the OsciPulse Instructions for Use. The subject will wear the device for a maximum of 3 hours while laying down. At the end of the study period the subject will receive an ultrasound scan of the deep venous system of the thigh/groin region to measure hemodynamics at a venous valve during immobility and during use of the OsciPulse device. Finally, the subject will participate in a questionnaire evaluation of their comfort and experience with the OsciPulse device. Participants will be compensated at \$50/ hour for their participation.

Part 2: After informed consent is obtained, baseline demographic and clinical data will be collected. The subjects will be randomized with equal allocation to either of the two treatment sequence groups:

- Group A (OsciPulse device then standard IPC device)
- Group B (standard IPC device then OsciPulse device)

For group A, the OsciPulse device will be applied to the subject on both legs in the first 3 hours. The subject will wear the device for the maximum number of hours as possible up to 3 hours. The [REDACTED] research team inquire with the subject if the device was removed during the testing period.. During the 3-hour period the study team will monitor for adverse events and a hemodynamic ultrasonography may be performed (when feasible) following the Ultrasound SOP. After 3 hours, the subject will complete the questionnaire evaluating the tolerability and safety of the device. In the following 3 hours, the standard IPC will be applied. Subjects will undergo the same procedure for compliance monitoring, adverse event monitoring, hemodynamic ultrasonography (when feasible), and questionnaire evaluation.

For group B, the same procedure will be performed but with the standard IPC in the first 3 hours and the OsciPulse device in the next 3 hours.

Participants will be compensated \$100 for their participation.

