4.6.2 Secondary Study Endpoints

- Percentage of time wearing the OsciPulse and standard IPC devices
- Ultrasonographic hemodynamic parameters (Change in venous centerline velocity in the femoral vein and volume of venous valve sinus reversing flow at the sapheno-femoral junction or other valve site imaged)

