6.2 Intervention Regimen

Part 1: The OsciPulse device will be worn by the subjects while they are in bed during the study duration. The subjects will be permitted to get up to use the restroom and for periods of stretching or walking for their comfort but will be encouraged to remain in bed for most of the study time. The device will be removed and reapplied by a clinical research coordinator or other trained personnel.

Part 2: The OsciPulse device should be worn by the subjects any time that they are in bed or seated in their room during the assigned 3-hour period. During operation, the device will inflate, compressing the calf 4-6 times per minute. The device will be worn during periods of subject immobility, including while sleeping. The device will be removed if the subject is getting out of bed and is ambulatory, or if the subject is receiving clinical care that requires that the device be removed as dictated by the clinical care team.

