6.6 Blinding

The intervention will not be blinded in this study

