7 STUDY PROCEDURES

Figure 3 Schedule of Study Procedures

Part 1:

Study Phase	Enrollment / Screening	Intervention and Assessment		
		-0.5 hrs	0 – 3 hrs	3 hrs
Screening and enrollment:				
Informed Consent	X			
Demographics	X			
Review inclusion/exclusion criteria	X			
Intervention				
OsciPulse device		X		
Assessment				
Ultrasound scan				X
Adverse Event Monitoring	X	X		X
Compliance Monitoring				X
Questionnaire				X

Part 2:

Study Phase	Enrollment / Screening	Intervention and Assessment				
		- 24 hrs	0 – 3 hrs	3 hrs	3(+/-1) – 6 hrs	6 hrs
Screening and enrollment:						
Informed Consent	X					
Review inclusion/exclusion criteria	X					

Study Phase	Enrollment / Screening	Intervention and Assessment			
		- 24 hrs	0 – 3 hrs	3 hrs	3(+/-1) – 6 hrs
Study Hour					
Demographics	X				
Laboratory Test Results		X			
Medical Record Review and History	X				
Vital Signs: BP, HR, RR	X				
Height and Weight	X				
Randomization of treatment sequence	X				
Intervention (Group A):					
OsciPulse device		X			
IPC device				X	
Intervention (Group B):					
IPC device		X			
OsciPulse device				X	
Assessment:					
Compliance monitoring*			X		X
Adverse Event Monitoring	X		X		X
Questionnaire(s)			X		X
Hemodynamic ultrasonography (when feasible)		X		X	

*Inquire with subject if the device was removed during the testing period

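### Percentage of time worn in Part 2 rests on end-of-period self-report with no described record of on and off times, so a small device difference in compliance could be masked or created by recall

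*Combined protocol and SAP*

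**What the plan says.** Section 3.2 makes compliance with OsciPulse against the standard IPC device a Part 2 secondary objective. Section 4.6.2 gives the endpoint as "Percentage of time wearing the OsciPulse and standard IPC devices". The Statistical Methodology entry in the Study Summary compares it by paired t-test.

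Section 8.8 says that research staff will collect it by "inquiring with the subject if the devices were removed for any period of time during the 3 hour study period". If a removal is reported, "staff will note the reason and duration of the interruption". Section 4.2.2 describes the same inquiry, and so does the footnote to the Part 2 schedule in Figure 3: "Inquire with subject if the device was removed during the testing period". Figure 3 marks compliance monitoring at 3 hours and at 6 hours, once per period. Section 8.6 adds: "The questionnaire will also consist of a question to evaluate compliance".

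Three other provisions bear on the point:

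- Section 6.6: "The intervention will not be blinded in this study".
- Section 6.2: "The device will be worn during periods of subject immobility, including while sleeping". It also provides for removal when the subject gets up or needs clinical care.
- Figure 3 and section 7.3.3 place the second period at 3(+/-1) to 6 hours.

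The accountability log in section 6.7 lists dates, not times. The documents describe no device usage log, scheduled observation of wear or staff-timed record of removal for Part 2.

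**The concern.** The endpoint is a duration divided by a duration, and the described method fixes neither from a clock. The numerator depends on what the subject reports at the end of the period about interruptions that may have been short or several. The denominator depends on a second period whose start may move by an hour either way.

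Random recall error widens the paired comparison. A recall error that differs on average between a novel and a familiar device shifts it. Randomising the sequence does not remove that shift, because the error belongs to the device and not to the period. Section 2.1 argues that discomfort with existing devices may weaken adherence, so a compliance comparison is likely to be read as support for the new device.

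**Working it through.** **The plan's own figures.** There is no sample-size or precision figure for compliance. The only such arithmetic is in section 9.2.3: 20 enrolled − 6 lost = 14 evaluable, which reproduces. Section 5.5 sets 15 to 20 evaluable subjects, so n = 15 and n = 20 are used below.

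**Inputs from the documents.** Period length 3 h = 180 min; second period 3(+/-1)–6 h; paired t-test.

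**Assumptions (the documents give none of these).** Two-sided α = 0.05; 80% power; SD of the true paired difference 10–30 points; recall error SD 5–30 min per period, independent between periods; average recall bias between devices 5–15 min.

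**Step 1: minutes to percentage points.** Points = 100 × minutes / 180.

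| Minutes | 5 | 10 | 15 | 30 | 60 | 90 |
|---|---|---|---|---|---|---|
| Points | 2.8 | 5.6 | 8.3 | 16.7 | 33.3 | 50.0 |

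**Step 2: denominator.** If the 6-hour end is fixed and the start moves between 2 and 4 hours, the second period lasts 120 to 240 min. The same 15-minute removal is then 15/120 = 12.5, 15/180 = 8.3 or 15/240 = 6.3 points. If instead the period always runs a full 3 hours after a shifted start, this uncertainty disappears. The text does not say which applies.

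**Step 3: random recall error.** Observed SD of the difference = √(SD_true² + 2 × SD_recall²), with SD_recall in points. For a recall SD of 10 min and a true SD of 20: √(400 + 2 × 5.56²) = 21.5. The difference detectable with 80% power at n = 15 is 0.778 × the observed SD:

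| Recall SD (min) | 0 | 5 | 10 | 15 | 30 |
|---|---|---|---|---|---|
| True SD 10: detectable (points) | 7.8 | 8.4 | 9.9 | 12.0 | 19.9 |
| True SD 20: detectable (points) | 15.6 | 15.9 | 16.7 | 18.1 | 24.1 |

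Recall alone (SD 5/10/15/30 min) adds a standard error to the mean difference of 1.0/2.0/3.0/6.1 points at n = 15 and 0.9/1.8/2.6/5.3 at n = 20.

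**Step 4: recall error that differs between devices.** With no true difference, the probability that the paired t-test rejects at n = 15 (nominal 0.05; SD is that of the observed difference) is:

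| Average bias between devices | SD 10 | SD 20 | SD 30 |
|---|---|---|---|
| 5 min (2.8 points) | 0.17 | 0.08 | 0.06 |
| 10 min (5.6 points) | 0.52 | 0.17 | 0.10 |
| 15 min (8.3 points) | 0.85 | 0.32 | 0.17 |

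Averaging over subjects does not shrink this bias. At n = 20 the 10-minute row becomes 0.66, 0.22 and 0.12.

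**Step 5: what it takes to produce such a bias.** Suppose 10–30% of subjects forget one removal of 15–30 min on one device only. That device's mean wear is then overstated by 0.10 × 8.3 = 0.8 to 0.30 × 16.7 = 5.0 points, or 1.5 to 9 min. A 10–15 minute average bias therefore needs somewhat more frequent or longer forgetting than this.

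**The case against.** The case for leaving the plan alone has real force. Both devices get the same inquiry, from the same subject, at the same point in each period, so recall error of equal average size cancels in the paired difference. Nothing in the documents shows that recall differs by device, or in which direction. The recall window is three hours, and section 5.1 requires Part 2 subjects to be mentally alert. Section 6.2 ties removals to getting out of bed or receiving care, so sleep is a weak reason for missing one. On mid-range assumptions random error costs little: the detectable difference moves from 15.6 to 16.7 points with a 10-minute recall SD. The V6 amendment entry shows that the compliance procedure was revised deliberately. Section 9.2.2 does not list compliance among the secondary endpoints, although 3.2 and 4.6.2 do. All of this limits the size of the problem. It does not supply a time record.

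Some stronger readings are not supported:

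- A reader might infer that recall error could be as large as any plausible device difference. The documents give neither a recall error nor a difference of interest, and a gap of 60 to 90 minutes (33 to 50 points) would not be matched by the errors assumed here.
- A reader might infer that everything hangs on one question. There is a staff inquiry with follow-up on reason and duration, plus a questionnaire item, though both are self-report at about the same time. Section 8.8 also does not say that the duration must come from memory alone.
- Acute illness is not an entry criterion, so it cannot be assumed to impair recall.
- Clock times cannot be declared absent from the study. Section 11.1 mentions visit worksheets that are not among the documents; all that can be said is that the plan describes no such times.
- Regular mid-period visits should not be assumed. Section 4.2.2 says "During the 3-hour period the study team will monitor for adverse events", but Figure 3 marks adverse-event monitoring only at screening, 3 hours and 6 hours.

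**Conclusion.** The concern holds in a limited form. A percentage-of-time endpoint is taken from end-of-period self-report by an unblinded subject, with no contemporaneous record described and an uncertain length for the second period. If average recall differed between devices by 10–15 minutes, the resulting 5.6–8.3 points could mask or create a device difference of about 5–10 points. A large difference would survive. That size rests wholly on assumed recall errors and SDs, and on the error differing by device. Because this is a secondary endpoint in a convenience-sample study of up to 20 subjects, priority is low to moderate.

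**What to change.** Amend section 8.8 and the Part 2 schedule in Figure 3, with its footnote, as follows:

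1. The coordinator writes down the clock time at which each device goes on and comes off, at start, changeover and end. The actual length of each period is the denominator.
2. At any bedside contact that already takes place within a period, such as the ultrasound or adverse-event questioning, staff note whether the device is on and the times of any interruption. No visits are added; extra ones might disturb sleep, which the questionnaire in 8.6 rates.
3. The subject's report is used for the remaining interruptions. Those durations are labelled as self-reported, and the results state how many rest on recall alone.

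The cost is a short time log, a wording change and a few minutes of coordinator time per subject. Interruptions between contacts will still depend on recall, which is why item 3 matters.

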9 STATISTICAL PLAN

9.1 Part 1

Part 1 of the trial is designed to test the tolerability of the OsciPulse system on healthy subjects for 3 hours prior to the 6-hour trial on patients. This is to determine if there are any immediate comfort issues that can be addressed prior to use in the clinical setting. Healthy volunteers are not the target population for the OsciPulse device and will have different tolerability for discomfort than hospital patients, but we feel that this test will be a qualitative analysis of the product prior to use in the target population. Subjects will indicate if the device caused 1) no discomfort, 2) mild discomfort, or 3) significant discomfort. **We will require that all three subjects indicate that there was not “significant discomfort” as reported on the subject questionnaire before continuing to Part 2.** This will be confirmed by the monitor prior to continuation to Part 2.

9.2 Part 2

Part 2 of the trial is designed to assess the tolerability and hemodynamic efficacy of the OsciPulse device in the clinical setting. The Primary endpoint is tolerability, which will be evaluated with questionnaires scored with a visual analog scale and will be directly compared between the OsciPulse device and a reference therapy device. Evaluable subjects will have completed the 6-hour study time that includes 3 hours with both therapies. This allows for the comparison between the therapies that makes the data quantitative rather than subjective. We will further measure hemodynamic efficacy through vascular ultrasound measurements of venous flow

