5.5 Total Number of Subjects and Sites

Part 1: Recruitment will end after 3 subjects have been enrolled.

Part 2: Recruitment will end when no fewer than fifteen (15) evaluable subjects and no greater than twenty (20) evaluable subjects have completed the clinical protocol. In the event a subject begins the clinical protocol, however, does not meet protocol defined requirements of "evaluable" status (see section 9.2, Part 2), the Sponsor reserves the right to replace that subject, which may result in greater than twenty (20) subjects being enrolled. In the unlikely event a disproportionate number of enrolled subjects do not meet the protocol defined requirements for reaching "evaluable" status, the Sponsor may pause the study to enrollment to reevaluate recruitment, inclusion and/or exclusion, or any other activity deemed necessary at the time.

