7.3.2 Part 2 Hour 1-3

- Application of OsciPulse device (Group A) or IPC device (Group B)
-
- Hemodynamic ultrasonography (when feasible)
- Questionnaire assessment at the end of 3 hours
- Adverse Events
- Laboratory Results

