7.3.3 Part 2 Hour 3(+-1)-6

- Application of IPC device (Group A) or OsciPulse device (Group B)
- Hemodynamic ultrasonography (when feasible)
- Questionnaire assessment at the end of 6 hours
- Adverse Events

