9.2.1 Primary Endpoint

The primary endpoint of this study is OsciPulse device tolerability compared to the current standard of care device. This endpoint will be measured by quantifying the differences in the responses to the questions on the subject questionnaire for each device. We will compare the visual analog scale ratings for the first 4 questions for each subject between the OsciPulse device and the reference therapy device. There are also 4 questions on the 6-hour questionnaire that ask the participants to directly compare the two devices, to determine the difference in tolerability. The ratings are reported in millimeters and the average differences between the responses will be statistically evaluated using a paired t-test.

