9.3 Subject Population(s) for Analysis

We will analyze the Protocol-compliant population defined as any subject who was randomized and received the protocol required investigational product exposure, the reference therapy product exposure, and completed the required questionnaires and ultrasound examinations. Subjects who are enrolled but do not complete the protocol requirements will not be analyzed.

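### The primary tolerability comparison is confined to subjects who complete both devices, and no planned analysis counts, by device, those who stop because a device is not tolerated

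*Combined protocol and SAP*

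**What the plan says.** Part 2 is a crossover with 3 hours on each device, and 9.2 and 9.2.1 make tolerability the primary endpoint.

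- **Who is analysed.** Section 9.2: "Evaluable subjects will have completed the 6-hour study time that includes 3 hours with both therapies". Section 9.3 defines one population: randomised, exposed to both products, with questionnaires and ultrasound done. It adds: "Subjects who are enrolled but do not complete the protocol requirements will not be analyzed".
- **Who is replaced.** For a subject who starts but is not evaluable, 5.5 says "the Sponsor reserves the right to replace that subject".
- **When ratings are taken.** Section 7.3.2: "Questionnaire assessment at the end of 3 hours". Section 7.3.3: "Questionnaire assessment at the end of 6 hours". Section 9.2.1: "There are also 4 questions on the 6-hour questionnaire that ask the participants to directly compare the two devices".
- **What is asked about removal.** The Figure 3 footnote reads "Inquire with subject if the device was removed during the testing period", with compliance marked at hours 3 and 6. Under 8.8, if a device came off, "staff will note the reason and duration of the interruption". Section 7.5 gives no follow-up after early termination.
- **Safety.** Section 9.2.7 plans adverse-event collection on all randomised subjects, and 9.2.2 totals events under each device. Section 9.3 makes no exception for safety, and 9.2.3 expects 14 subjects with evaluable tolerability and safety data.

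**The concern.** Leaving because a device cannot be tolerated is itself a tolerability result. Under 9.2 and 9.3 it removes the subject from the analysis of tolerability, and 5.5 may put someone else in that place. The primary comparison can thus be selected on its own outcome.

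Two things are at stake. First, if stopping for intolerance is more frequent on one device, the remaining ratings make that device look better than it is. Section 4.1 hypothesises equivalence with the standard device, so a real disadvantage could be pulled towards no difference, or an advantage could appear where none exists. Second, the number of subjects who could not tolerate each device would not be reported. Nothing in sections 4.6 or 9 tabulates it. The adverse-event total counts events rather than stops, and wear time is not planned by reason for removal.

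**Working it through.** **1. The plan's own figure.** Section 9.2.3 allows 6 losses among up to 20 enrolled: 20 − 6 = 14, as stated. The reasons it lists are discharge, surgery, loss of consciousness and death; intolerance is not among them. The sample is one of convenience, so there is no power calculation to reproduce.

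**2. Tracing a subject who cannot tolerate a device.**

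| Course | VAS comparison | Counted as a stop? |
|---|---|---|
| Leaves in period 1 | Excluded: second device never rated | No |
| Leaves in period 2 | Excluded: no hour-6 questionnaire | No |
| Removes device early, stays, rates both | Unclear | No; reason noted under 8.8 but not tabulated |

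The third row is unclear because 9.2 requires 3 hours with both therapies, 9.3 asks only for the protocol-required exposure, 4.2.2 describes wear for as long as possible up to 3 hours, and 8.5 and 8.8 foresee removal within the study.

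**3. Size of the shift.** All inputs here are assumptions. Let X and Y be the ratings of the stopped and the other device on one VAS question, with equal variances and correlation ρ, and D = X − Y with SD 20 mm. A proportion p stops, on one device only, and all stoppers are excluded.

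- *Strong selection.* The worst p are removed exactly. The shift in SD units is φ(z)/(1 − p), with z the upper p point of the normal: 0.109, 0.195 and 0.350 at p = 0.05, 0.10 and 0.20. Period-2 leavers select on D. Period-1 leavers select on X alone, so their shift is multiplied by corr(X, D) = √((1 − ρ)/2) = 0.71 at ρ = 0. With half in each period the factor is (0.71 + 1)/2 ≈ 0.854. Shift = 20 × 0.854 × (0.109, 0.195, 0.350) = 1.9, 3.3 and 6.0 mm.
- *Moderate selection.* Logistic stopping with slope 1 per SD gives 0.047, 0.091 and 0.173. At ρ = 0.5 the factor is (0.50 + 1)/2 = 0.75. Shift = 0.7, 1.4 and 2.6 mm.
- *Weak selection.* Logistic with slope 0.5, on X alone in both periods, gives 0.025, 0.049 and 0.096. At ρ = 0.5 the factor is 0.50. Shift = 0.25, 0.5 and 1.0 mm.

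| Stopping | Shift, weak to strong | Chance of a significant false advantage |
|---|---|---|
| 5% | 0.2-1.9 mm | about 3-5% |
| 10% | 0.5-3.3 mm | about 3-10% |
| 20% | 1-6 mm | about 4-25% |

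The last column is simulated: 20 randomised, no replacement, no true difference, two-sided 5% paired t-test on one question. Without selection it is 2.5%.

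**4. Scale.** The standard error of the mean difference is 20/√20 = 4.5 mm with 20 subjects and 20/√14 = 5.3 mm with 14. At 5-10% stopping the shift is below it; at 20% it runs from well below to slightly above. With equal stopping rates and the same selection on both devices, the shift is zero.

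**5. What a count would show.** Exact 95% intervals over 20 exposed: 0 stops, 0-16.8%; 2 stops (10%), 1.2-31.7%; 4 stops (20%), 5.7-43.7%. The intervals are wide, but a population of completers contains no one who left, whatever the true number.

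**The case against.** The strongest reply is that the effect may be negligible. No document gives an intolerance rate, the foreseen losses are unrelated to comfort, and wear is only 3 hours per device. At 5-10% stopping the shift is smaller than the standard error, and the 25% false-advantage figure needs the worst fifth to be removed exactly. This stands, and it limits the severity.

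Several stronger readings are tempting, and the documents do not support them.

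- *The analysis must favour the less tolerated device.* This holds only if stopping for intolerance is more frequent on that device.
- *Anyone who removes a device early is excluded.* If 4.2.2 sets the required exposure, such a subject may be evaluable and adds no shift.
- *Safety data on leavers are discarded.* Section 9.2.7 plans collection on all randomised subjects. The fault is that 9.3 and 9.2.3 do not fit it.
- *The reason for leaving is lost for good.* Section 10.2 has subjects questioned and the record screened, 10.3 asks in event narratives whether the intervention was discontinued, and 11.3 requires deviations to be documented with a root cause. Some reasons may be captured there. Discomfort not recorded as an adverse event may be missed, and whether a voluntary departure is a deviation is arguable.

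None of these records feeds a planned analysis, so the gap remains.

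**Conclusion.** The point holds and should be fixed, though it does not by itself invalidate the trial. As written, a subject who leaves before rating both devices because one is not tolerated is outside the primary comparison, and no planned analysis counts such stops by device.

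The bias is conditional on unequal stopping. Its size rests entirely on the assumed 20 mm SD, one-sided stopping, exclusion of every stopper and the form of selection; if some stoppers stay and rate both devices, it is smaller. The firmer ground is the missing count: a direct tolerability result would go unreported, and the reasons behind it may not be recorded systematically.

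Two sets of passages must be reconciled: 9.2 with 4.2.2, 8.5 and 8.8 on who is evaluable, and 9.3 and 9.2.3 with 9.2.7 on safety.

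**What to change.** 1. **Define sets by endpoint in 9.3.**
   - Safety: all randomised subjects, as in 9.2.7, with events counted by the device worn at onset and events before the first device listed separately. Align 9.2.3 and 9.3.
   - Tolerability VAS: all subjects with a rating for both devices, whatever the hours worn and whether or not ultrasound was done. Keep the completer analysis as supportive. State in 9.2 whether evaluable means 3 assigned hours or 3 hours worn.
2. **Report stops beside the VAS comparison.** For each device, over all exposed subjects including any replaced under 5.5, give the number and proportion, with exact 95% confidence interval, who stopped for discomfort or an adverse event. Show other and unknown reasons separately. This is needed because the VAS set still omits those who leave before rating the second device.
3. **Collect the reason when it arises.** At early removal or departure, ask the existing 8.8 question and offer the existing questionnaire to subjects who have not withdrawn consent. Align 7.5, 8.8 and Figure 3. Section 7.4.1 can stand.

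A sign test that scores a stopped device as the worse one is at most an optional, clearly labelled worst case: for a period-1 stopper it assumes a preference for a device never worn.

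**Cost.** A protocol amendment with IRB approval (11.6), rewording of these sections and a few extra questions at the bedside. Some ratings will rest on less than 3 hours of wear, and some reasons will stay unknown, mainly where consent is withdrawn.
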